6 TRIAL ENTRY

After screening, the following will be checked prior to recruitment:

- Participant has provided consent and;
- Confirmation that the eligibility criteria have been met.

If eligibility is confirmed, the patient can be randomised into the trial.

6.1 Randomisation

As soon as the patient is considered eligible the Investigator should enter the patient into the trial by completing the Randomisation Form on the electronic Remote Data Capture (eRDC) system below.

<https://www.cancertrials.bham.ac.uk>

Investigators must be registered with the Trial Office before they are permitted to enter patients into the trial.

The site is asked to confirm the patient's eligibility, and provide the following information:

- Name of the investigator responsible for the care of the randomised patient
- Patient's initials and date of birth

- Date of consent
- Disease cohort (or sub-cohort for the lymphoid malignancies)
- Type of SARS-CoV-2 vaccine previously received
- SARS-CoV-2 anti-spike antibody test performed and level (AU/ml)
- Whether the patient participated in a prior SARS-CoV-2 vaccine immune response study (including study acronym and unique subject identifier)

6.1.1 Main Study Randomisation

For the main study randomised comparison, patients will be randomised in a 1:1 ratio using a minimisation program (developed by the CRCTU) with the following stratification variables:

- Disease cohort: solid cancer; lymphoid malignancies; immune-mediated rheumatic diseases; end stage kidney disease; chronic liver disease; gastrointestinal disease on immune suppressive therapy; haematopoietic stem cell transplant; primary immunodeficiency; and CAR-T Cell therapy
- Prior SARS-CoV-2 vaccine type: AstraZeneca; Pfizer; Moderna; Other
- SARS-CoV-2 vaccine response: antibody non-responders or antibody low-responders defined as:
 - o Antibody non-responders: Defined as SARS-CoV-2 anti-spike antibodies below the level of detection using the PHE Roche platform <0.8 AU/ml [or equivalent]); and
 - o Antibody low-responders: Defined as SARS-CoV-2 anti-spike antibodies ≥ 0.8 and <400 AU/mL using the PHE Roche platform [or equivalent].

Patients will be randomised to receive:

- Arm 1: Pfizer SARS-CoV-2 Vaccine; or
- Arm 2: Moderna SARS-CoV-2 Vaccine.

6.1.2 Sub-study Randomisation

For the sub-study randomised comparison, patients will be randomised in a 1:1:1 ratio using a minimisation program with the following stratification variables:

- Lymphoid malignancies sub-cohort diseases:
 - o Aggressive B-NHL
 - o CLL
 - o Hodgkin Lymphoma

- o Indolent B NHL
- o Myeloma
- Prior SARS-CoV-2 vaccine type: AstraZeneca; Pfizer; Moderna; Other
- SARS-CoV-2 vaccine response: antibody non-responders or antibody low-responders as defined above.

Patients will be randomised to receive:

- Arm 1: Pfizer SARS-CoV-2 Vaccine; or
- Arm 2: Moderna SARS-CoV-2 Vaccine; or
- Arm 3: Novavax SARS-CoV-2 Vaccine.

6.1.3 Following Randomisation

The randomisations are not blinded and, therefore, both participants and the Site Research Team will know which treatment has been allocated to the patient.

At the end of the randomisation procedure, the participant will be allocated to the appropriate arm and given a unique trial number.

Where applicable the Responsible Pharmacist (e.g. where the participant is randomised to Novavax) will be notified by a member of the site research team that a patient has been entered onto the trial.

The Baseline Form* should be completed on the eRDC system.

A copy of the Randomisation Confirmation Report, signed Informed Consent Form, and Eligibility Checklist should be filed within the Investigator Site File.

** Where the participant took part in OCTAVE, completion of the Baseline Form will not be required for some disease cohorts as data will be obtained from the OCTAVE database and the OCTAVE Case Report Form (CRF) used for monitoring purposes*

7 TRIAL TREATMENT

7.1 Investigational Medicinal Products

The following SARS-CoV-2 vaccines are regarded as Investigational Medicinal Products (IMPs) for this trial:

- Pfizer SARS-CoV-2 vaccine
- Moderna SARS-CoV-2 vaccine

- Novavax SARS-CoV-2 vaccine

7.1.1 Pfizer SARS-CoV-2 Vaccine

The SARS-CoV-2 vaccine BNT162b2, manufactured by Pfizer, is an mRNA vaccine that encodes trimerised SARS-CoV-2 spike glycoprotein. mRNA vaccines exploit the host's cells to make the target protein.

BNT162b2 is approved for use under a temporary authorisation of the supply of an unlicensed vaccine; regulation 174 of the Human Medicines Regulations 2012.

Vaccine should be ordered from PHE using IMMFORM. It will not be labelled as IMP for this trial and the product will be used as supplied by the manufacturer (as for national supply). Vaccine accountability will be in accordance with local Trust policy.

Each pack of the Pfizer vaccine contains 195 vials which after dilution contain 6 doses per vial.

Vaccine should be stored and prepared as specified in the Information for UK Healthcare Professionals.

See the OCTAVE-DUO Pharmacy Manual for additional information.

7.1.2 Moderna SARS-CoV-2 Vaccine

The Moderna SARS-CoV-2 vaccine, manufactured by Moderna Biotech, is an mRNA vaccine which encodes for the full-length SARS-CoV-2 spike protein modified with 2 proline substitutions within the heptad repeat 1 domain (S-2P) to stabilise the spike protein.

Moderna SARS-CoV-2 vaccine has been authorised by MHRA in Great Britain (consisting of England, Scotland and Wales).

Vaccine should be ordered from PHE using IMMFORM. It will not be labelled as IMP for this trial and the product will be used as supplied by the manufacturer (as for national supply). Vaccine accountability will be in accordance with local Trust policy.

The vaccine is supplied in multidose vials which contain 10 doses of 0.5 mL.

Vaccine should be stored and prepared as specified in the Summary of Product Characteristics (SmPC).

See the OCTAVE-DUO Pharmacy Manual for additional information.

7.1.3 Novavax COVID-19 Vaccine

The SARS-CoV-2 vaccine NVX-CoV2373, manufactured by Novavax, was constructed from the full-length wild-type pre-fusion trimers of SARS-CoV-2 spike glycoprotein.

NVX-CoV2373 is currently unlicensed in the UK. It will be supplied pre-labelled as clinical trial supplies by Novavax. See the OCTAVE-DUO Pharmacy Manual for details of accountability arrangements.

Protocol

Vaccine will be supplied labelled as clinical trials supplies by Novavax. Ordering procedures are described in the Pharmacy Manual.

The vaccine is supplied in 10 dose vials. Vaccine should be stored and prepared as specified in the Investigator Brochure (IB).

7.2 Administration of Investigational Medicinal Products

Participants should receive their re-boost vaccine a minimum of 14 days after their second booster.

The administration of the Pfizer and Moderna SARS-CoV-2 vaccines should be postponed in individuals suffering from acute severe febrile illness. The presence of a minor infection and/or low-grade fever should not delay vaccination.

7.2.1 Pfizer SARS-CoV-2 Vaccine

The dose of Pfizer vaccine is 30µg contained in 0.3ml of the diluted vaccine (standard dose) given intramuscularly.

Vaccine should be prepared and administered in accordance with the Information for UK Healthcare Professionals.

Participants should be observed for 15 minutes following vaccination.

7.2.2 Moderna SARS-CoV-2 Vaccine

The dose of Moderna vaccine is 0.5ml, containing 100 µg of messenger RNA (mRNA), given intramuscularly.

Vaccine should be prepared and administered in accordance with the SmPC.

Participants should be observed for 15 minutes following vaccination.

7.2.3 Novavax SARS-CoV-2 Vaccine

A dose of 5 µg recombinant spike protein with 50 µg Matrix-M1 adjuvant (0.5ml) will be given intramuscularly.

Participants should be observed for 15 minutes following vaccination.

7.3 Assessments

Assessments should be carried out as detailed below.

7.3.1 Screening

For the randomised sub-study only, a negative urine dipstick pregnancy test should be performed to confirm eligibility at screening for women of child-bearing potential.

For the solid cancer, haematopoietic stem cell transplant and CAR-T cell therapy disease cohorts only, a SARS-CoV-2 spike antibody response can be measured as a screening assessment using one of the

assays listed in Appendix 1, or another assay with the prior agreement of the Trial Management Group (TMG).

7.3.2 Baseline

Participants will be required to attend clinic for the collection of the baseline research sample which must be collected prior to re-vaccination (see Section 7.5 for details of sample collection). Samples can be collected on the day of vaccination as long as this is prior to the re-boost vaccination or up to 2 weeks (14 days) in advance.

The participant should be given a Participant Diary Booklet and instructed on how to complete the diary sheets. Participants should be advised to complete one column per day for 3 weeks. They should be asked to return the Booklet at the day 21 visit.

Data (including medical history, disease history and treatment, prior COVID-19 infection and vaccination history) will be collected on the Baseline Form. These data may be collected retrospectively from the participants' medical records. Where the participant took part in the OCTAVE trial these data will be obtained from the OCTAVE trial database and this information does not need to be provided by the site.

A Research Blood Sample Collection Form should also be completed.

7.3.3 Re-Boost vaccination

Participants will be required to attend clinic for re-boost vaccination (see Section 7.3.3).

The following forms should be completed at this time point:

- Treatment Form (documenting disease specific treatment)
- Vaccination Form

7.3.4 Post Re-boost vaccination

Participants will be required to attend clinic for the collection of the post re-boost vaccination research blood sample which must be collected on day 21 (as a minimum) or within an additional 14 days (by day 35). See Section 7.5 for details of research blood sample collection.

Participant Diaries should be collected from the participant and used as a guide to complete the Adverse Event Form.

The following forms should be completed at this time point:

- Adverse Event Form
- Research Blood Sample Collection Form

7.3.5 Three Month Follow-up

Where possible participants will be followed up in accordance with standard clinical practice for the relevant disease cohort and data will be collected retrospectively from clinic records 3 months after re-boost vaccination. Where participants do not attend for a routine clinic visit, data may be collected following an additional telephone follow-up call.

A Follow-up Form should be completed.

7.4 Contraception and Pregnancy for Participants in Randomised Sub-study

There is no evidence from animal studies that the SARS-CoV-2 vaccines used in this trial cause direct or indirect harmful effects with respect to pregnancy, embryo/foetal development, parturition or post-natal development for any of the COVID-19 vaccines included in this trial. However there is limited experience using SARS-CoV-2 vaccines in pregnant women and particularly with regard to Novavax. Therefore female participants of childbearing potential taking part in the randomised sub-study are required to ensure that they or their partner use acceptable effective contraceptive methods until 3 months after the re-boost immunisation.

Acceptable birth control methods include:

- Combined (oestrogen and progestogen containing) hormonal contraception associated with inhibition of ovulation
- Progestogen-only hormonal contraception associated with inhibition of ovulation
- Intrauterine device (IUD)
- Intrauterine hormone-releasing system (IUS)
- Bilateral tubal occlusion
- Vasectomised partner
- Sexual abstinence
- Progestogen-only oral hormonal contraception, where inhibition of ovulation is not the primary mode of action
- Male or female condom with or without spermicide
- Cap, diaphragm or sponge with spermicide

7.5 Sample Collection and Analysis

7.5.1 Collection

Sites will be provided with kits for the collection of the research blood samples.

Up to 55 ml of blood will be collected from participants at any one visit comprising whole blood, serum plasma, and peripheral blood mononuclear cells (PBMC) where possible. Samples will be collected at the following time points:

- Pre-vaccine (baseline) -14 to day 0 (but must be given prior to re-vaccination)
- 21 (+14) days post-re-boost vaccination

See Table 1 for further details on samples types collected and storage conditions.

Samples must be received by Oxford Immunotec within 32h of collection. The remaining samples will be shipped in batches to the relevant coordinating laboratory. Sites will be provided with details of which laboratory to send the samples to at the time of shipment. Full details of the sample collection and processing procedure are included in the Laboratory Manual.

Table 1: Details of Sample Collection and Storage

Sample Type	Collection Tube	Volume	Laboratory Analysis	Aliquots	Sample Storage
Whole Blood	Tempus RNA	3ml	RNA	None	-80°C
Whole Blood	EDTA	9ml x minimum of 2 (maximum of 3)	Cellular immunoassays & DNA	4 x 500ul (as PBMCs) † 5 x 700ul (as Plasma)	-80°C for Plasma (long-term) and PBMCs (short-term), then liquid nitrogen or -150 °C; depends on site (long-term)
Serum	Serum separator tubes (SST)	5ml x 2	Immunoassay; ELISA and virus neutralisation assays	10 x 400ul	-80°C
Whole Blood	Lithium Heparin*	6ml x 2	ELISpot assay	None	None

* Two 6ml lithium heparin tubes will be shipped to Oxford Immunotec at ambient temperature

† PBMCs will be collected where possible but are not mandated

7.5.2 Analysis

Laboratory analysis to be conducted on the samples will include:

- Assessment of quantitative antibody responses to SARS-CoV-2 spike and nucleocapsid antigens will be undertaken by the UK Health Security Agency Laboratories at Porton Down.
- Assessment of IFN-g T cell responses to SARS-CoV-2 antigens in an ex vivo ELISpot assay, to be undertaken by Oxford Immunotec.
- Assessment of neutralising antibody responses to SARS-CoV-2 antigens be undertaken at the laboratories at the University of Glasgow.
- Assessment of fine specificity of T cell (ELISpot and Flow cytometric assays) will be performed by laboratories at the University of Oxford and Imperial College London.
- Assessment of IgG/IgM/IgA responses to SARS-CoV-2 antigens and other relevant season antigens will be undertaken by the laboratories at the University of Glasgow.

This is not an all-inclusive list, additional assays will be included as more information becomes available about the immune response elicited by SARS-CoV-2 vaccination.

Principal Investigators will be provided with the results of their patients' assessment of immune response to at the end of the trial. Participants should be provided with the results on request.

7.5.3 Future Research and Biobanking

Any samples remaining at the end of the trial will be banked in a Human Tissue Authority (HTA) licenced biobank. The samples and data will be made available for future research in other ethically approved studies (see Section 13.3 and Section 18 for further details).

7.6 Data Linkage

The participant's NHS number or CHI number will be collected to allow linkage with national data registries such as NHS Digital, UK Health Security Agency, the Information Services Division (part of NHS Scotland), or the electronic Data Research and Innovation Service (eDRIS). For the haematopoietic stem cell transplant cohort the British Society of Blood and Marrow Transplantation (BSBMT) registry identification (PROMISE ID) will also be collected, where participants have also consented to collection of data within this registry, to allow for data linkage. Data linkage will allow for long-term follow-up data to be collected and it will provide a more complete profile of the participants' health and disease without increased data collection burden to the NHS.

7.7 Participant Withdrawal

Participants may withdraw consent at any time during the trial. For the purposes of this trial two types of withdrawal are defined:

- The participant would like to withdraw from the trial but is willing to be followed up as standard (i.e., the patient has agreed that data can be collected at disease cohort specific clinic visits and used in the analyses); or
- The participant would like to withdraw from the trial entirely and is not willing to be followed up for the purposes of the trial (i.e., only data and blood samples collected prior to the withdrawal of consent can be used in the trial analysis) – withdrawal of consent.

The details of withdrawal (date, reason and type of withdrawal) should be clearly documented in the source data. A Withdrawal of Consent Form should be completed to notify the Trial Office of the participant's withdrawal from the trial.

8 ADVERSE EVENT REPORTING

The collection and reporting of Adverse Events (AEs) will be in accordance with the Medicines for Human Use Clinical Trials Regulations 2004 and its subsequent amendments. Definitions of different types of AE are listed in Appendix 2. The seriousness and causality (relatedness) of all AEs experienced by the participant should be assessed with reference to the relevant IMP information as specified in Section 7.1.

8.1 Reporting Requirements

8.1.1 Adverse Events

All medical occurrences which meet the definition of an AE should be reported, with the exception of abnormal laboratory findings which should only be reported if they are CTCAE grade 3 or above.

If a laboratory abnormality is one component of a diagnosis or syndrome, then only the diagnosis or syndrome should be recorded as an AE.

Pre-existing conditions should only be reported if the condition worsens by at least one CTCAE grade.

Participants will be provided with a Diary Booklet to aid in the capture of AEs. If the participant does not return the Booklet, they should be asked to provide details of any AEs they experienced. Details of AEs recorded by the participant or noted by the Research Team will be captured on an AE Form.

8.1.2 Serious Adverse Events

Investigators should report AEs that meet the definition of an SAE and are not excluded from the reporting process as described in Section 8.1.2.1. These events should be reported on an SAE Form after first becoming aware of the event as described in Section 8.3.1.2.

8.1.2.1 Events that do not require reporting on a Serious Adverse Event Form

The following events should not be reported on an SAE Form:

- Hospitalisations for:
 - o Disease treatment
 - o Receipt of supportive care for disease treatment related toxicities (e.g. neutropenic sepsis, vomiting for cancer participants)
 - o Disease progression (unless there is concern this has been exacerbated by vaccination)
 - o Pre-planned elective procedures unless the condition worsens

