8.3.2 OCTAVE-DUO Trial Office

On receipt of an SAE Form, causality and expectedness will be determined by a Clinical Coordinator. An SAE judged by the investigator or Clinical Coordinator to have a reasonable causal relationship with the trial medication will be regarded as a Serious Adverse Reaction (SAR). If the event meets the definition of a SAR that is unexpected (i.e., is not listed in the Reference Safety Information) it will be classified as a Suspected Unexpected Serious Adverse Reaction (SUSAR).

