8.3.3.5 Data Monitoring Committee

The independent Data Monitoring Committee (DMC) will review all SAEs.

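### Two of the four hospitalisation exclusions in Section 8.1.2.1 lack the vaccination-concern exception, so admissions of uncertain cause bypass the SAE Form route

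*Protocol*

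**What the plan says.** Section 8.1.2 makes SAE reporting conditional: "Investigators should report AEs that meet the definition of an SAE and are not excluded from the reporting process". The exclusions are in Section 8.1.2.1. Its heading speaks only of events that need not be reported, but the body is an instruction: "The following events should not be reported on an SAE Form". The list opens with "Hospitalisations for" and has four items:

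- disease treatment, with no exception;
- "Receipt of supportive care for disease treatment related toxicities (e.g. neutropenic sepsis, vomiting for cancer participants", with no exception;
- "Disease progression (unless there is concern this has been exacerbated by vaccination";
- pre-planned elective procedures, with an exception if the condition worsens.

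The central safety process starts from the form. Section 8.3.2 says: "On receipt of an SAE Form, causality and expectedness will be determined by a Clinical Coordinator". Section 8.3.3.5 says that the DMC "will review all SAEs". Section 8.3.3.6 times the report to the Novavax manufacturer from the Trial Office's receipt of the SAE.

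**The concern.** The protocol recognises that vaccination might worsen a participant's underlying condition, but it applies that caution to one item only. In this population an admission soon after the dose often has more than one plausible cause. Neutropenic sepsis or vomiting in a patient on cancer treatment may come from that treatment, from the vaccine, or from both. An admission to treat worsening rheumatic, bowel or liver disease can be read as disease treatment, which is not reportable, or as progression with a vaccination concern, which is. Section 8.1.2.1 gives no order of precedence.

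In such cases the site settles the attribution alone and then, following the wording, withholds the form that would bring a second assessor. What is at stake is the completeness of the SAE data used for expedited reporting and DMC review. One of the three vaccines is described as unlicensed in the UK.

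**Working it through.** No arithmetic beyond the reporting windows applies, so the sections are set side by side.

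**Step 1: the exception.** Of the four items in Section 8.1.2.1, one has a vaccination-concern exception (progression), one has a different exception (elective procedures), and two have none (disease treatment; supportive care for treatment toxicity).

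**Step 2: what depends on the form.**

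- *Second causality opinion.* Section 8.3.2 classes an SAE as a SAR if either the investigator or the Clinical Coordinator sees a reasonable causal link. The coordinator acts when a form arrives, so without one the second opinion is lost.
- *SUSAR classification.* This needs expectedness, which Section 8.3.2 also assigns to the coordinator on receipt of the form.
- *Site route.* Section 8.3.1.2 describes no way for a site to report an SAE other than the SAE Form.
- *Manufacturer and DMC.* Sections 8.3.3.5 and 8.3.3.6 act on SAEs that have reached the Trial Office.

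**Step 3: what remains without the form.**

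- The opening of Section 8 requires seriousness and causality to be assessed for all AEs.
- Section 8.1.1 requires all AEs to be reported, including a pre-existing condition that worsens by one CTCAE grade. Section 8.1.2.1 restricts the SAE Form only, so the AE Form still applies.
- Section 13.6 gives the DMC patient-safety analyses, not only individual SAEs.
- Section 8.2 requires expedited reporting of SAEs that are possibly related and unexpected.

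**Step 4: how far these backstops reach.**

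- The Section 8.2 rule lifts the time limit. It does not say that it overrides Section 8.1.2.1, and it depends on expectedness, which is judged only once a form is received.
- Table 2 names onset date and grade for the AE Form, not causality. The entry is worded as a non-exhaustive list, so causality may still be collected.
- Table 2 makes the AE Form due within 2 weeks of vaccination. Section 7.3.4 has it completed at the post-vaccination visit, which is at day 21 or later.
- Section 8.3.3.3 sends AE details to the MHRA on request only.
- Under Section 8.2, AEs are collected to day 21 and SAEs to day 28. 28 − 21 = 7, so an excluded admission on days 22 to 28 goes on neither the AE Form nor the SAE Form.

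**The case against.** The strongest reply is that each item, read narrowly, does its own job. Disease treatment would mean admission to give planned treatment. Worsening disease would fall under progression, which already has the exception; a broader reading of disease treatment would leave that exception with nothing to do. The supportive-care item covers only toxicity of the disease treatment, so a fever attributed to the vaccine lies outside it. The list concerns hospitalisation only, so events that are serious on another Appendix 2 criterion are not named. Sections 8.3.1.1 and 8.3.1.2 refer to completion guidelines that are not available here and may deal with uncertain attribution.

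Much of this stands, and it rules out several stronger readings:

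- A reader might infer that a vaccine-related admission never receives causality or DMC review. The opening of Section 8, Section 8.1.1 and Section 13.6 contradict that.
- A reader might infer that any fever or vomiting after the dose, or any graft rejection, is excluded. The supportive-care item is limited to treatment toxicity. Rejection is not named, and placing it under disease treatment is a matter of interpretation.
- A reader might infer that the safety objective in Section 2.1.3 is answered from filtered data. That objective is exploratory, and Section 2.2.3.1 meets it with a descriptive analysis of AEs, which are reported separately from the SAE Form.

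The reply does not remove the case of mixed or uncertain attribution. The narrow reading is reasonable, but the text does not state it, and a site following the broader reading would also be following the protocol.

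**Conclusion.** The point holds as a specific gap in the safety-reporting rules. For admissions of mixed or uncertain cause, two of the four exclusions divert the event from the normal route to central causality and expectedness review, SUSAR classification, the manufacturer report and DMC review of SAEs. The backstops are partial and are weakest on days 22 to 28.

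The number of affected admissions is unknown, because the protocol gives no rates. A reader might size the problem by adding the recruitment targets of the cohorts in which one of the two items could apply. That counts participants, not events, and it overstates exposure: Section 4.2 excludes patients with aggressive B-NHL or Hodgkin lymphoma who are on systemic treatment or within 4 weeks of completing it, and CAR-T participants are defined by past treatment.

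The conclusion assumes that sites follow the wording of Section 8.1.2.1 and that the completion guidelines add no overriding instruction. It is worth correcting before further reporting, but it does not show that any signal has been lost.

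**What to change.** Move the existing qualifier from the progression item to the head of the list in Section 8.1.2.1, so that it governs every item. For example: *The following hospitalisations should not be reported on an SAE Form, unless there is concern that the event was caused or exacerbated by vaccination.* This also settles the overlap between disease treatment and progression, since both would then give the same answer. A suspected event on days 22 to 28 would return to the SAE Form.

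Then reconcile the opening of Section 8 with Sections 8.1.2, 8.1.2.1, 8.2 and 8.3.2. In particular, state whether the expedited rule in Section 8.2 applies to the hospitalisations listed in 8.1.2.1. Bring the SAE Form Completion Guidelines into line.

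The cost is a short amendment, a guideline update and some additional SAE Forms. Their number cannot be estimated from the protocol, but the qualifier limits them to admissions where someone has a vaccination concern.
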